V-safe data is collected, managed, and housed on a secure server by Oracle. Through Health and Human Services (HHS), Oracle has donated IT services to any agency conducting COVID-19 related activities. Oracle is providing IT support for the v-safe After Vaccination Health Checker platform. All data participants report voluntarily into the v-safe After Vaccination Health Checker platform are collected, stored, processed, and transmitted in Federal Risk and Authorization Management Program (FEDRAMP) approved infrastructure environment (23).

CDC ISO data managers will create a dataset for the pregnancy registry call center which includes only those participants who report potential pregnancies. As previously described, the data elements reported directly by participants into the v-safe After Vaccination Health Checker platform that will be shared with the COVID-19 Vaccine Pregnancy Registry are limited to those that allow the pregnancy registry interviewers to reach out to those participants to confirm eligibility through review of dates of pregnancy and receipt of vaccine and to inquire about their willingness to participate in the pregnancy registry. Data acquired through the interviews following this enrollment (including data provided verbally during phone calls and any data obtained through review of select medical records if participants consent) will be stored on an internal CDC server. Data from all components of the pregnancy registry may be combined into a master dataset behind the CDC firewall using unique identification numbers assigned at registration.

Pre-approved CDC investigators and data managers, including CDC contractors, will be the only individuals with access to the full data. All electronic documents, data sets, and files relevant to the project will be stored on network folders with restricted access on CDC computers. The pregnancy registry team at CDC will be primarily responsible for data management activities, including data extraction, documentation and archival of a final data set. The archive will include the protocol, statistical programs, human subjects review documents, statistical output, analytical data sets, and manuscripts. Data sharing plans will be developed at the completion of data collection.

Human subject considerations and confidentiality:

This protocol has received a non-research determination through standard CDC review processes.

CDC is the lead site and surveillance data will include collection of personal identifiable information (PII). This data will be collected for public health surveillance, not for research purposes. PII will not be included in any pregnancy registry analyses, manuscripts, or datasets shared externally. Participation is voluntary and individuals self-enroll at the time of the initial telephone call during which eligibility for the registry is determined. Participants can opt-out of the pregnancy registry at any time and their data will only be used for the time they were considered an active participant. In addition, this activity presents minimal risk to participants, and use of participant data for this purpose will not adversely affect participants' rights or welfare.

308(d) Assurance of Confidentiality Protection was awarded to the COVID-19 Vaccine Pregnancy Registry on April 25, 2022 (references 42 USC 242(k), and 42 USC 242(m)).

Duration:

The anticipated duration of participant's and their infant's inclusion in the pregnancy registry will be up to two years after vaccination, depending on the time point in pregnancy that a person is exposed to vaccine. The decision to discontinue the pregnancy registry program or to modify pregnancy registry procedures to scale back active telephone follow-up will be made in consultation with key stakeholders including the CDC COVID-19 Vaccine Task Force leadership, Immunization Safety Office (ISO) leadership, and FDA.

Limitations and challenges:

Limitations and challenges for the COVID-19 Vaccine Pregnancy Registry include the potential for limited enrollment and retention in the program given its voluntary nature. It might be difficult to contact pregnant and postpartum persons by phone, and to obtain medical records on pregnant persons and infants. Furthermore, vaccinated pregnant persons who choose to participate in both the v-safe After Vaccination Health Checker and the COVID-19 Vaccine Pregnancy Registry might be different from those who do not; therefore, rates of outcomes reported by pregnancy registry participants might not be generalizable to the full population of pregnant COVID-19 vaccine recipients. However, it is possible to compare characteristics of pregnancy registry participants with those of representative samples of pregnant people within the United States. Similarly, pregnant persons who choose to participate in the pregnancy registry might be those who are more likely to have concerns or have experienced adverse events. This potential bias may be minimized by the prospective nature of this surveillance system, by review of medical records and accurate characterization of events. Additionally, a sensitivity analysis examining only outcomes among those who were enrolled and monitored before an adverse pregnancy or birth outcome occurred will be performed. Finally, the information provided by pregnancy registry participants for up to two years after vaccination might be impacted by recall bias, specifically among those for whom we are unable to obtain medical records.

Dissemination of information:

Safety profile information from the pregnancy registry may be presented to the Advisory Committee on Immunization Practices (ACIP) subgroups (such as the Vaccine Safety Technical Subgroup [VaST]), ACIP meetings and other meetings that are requested. Further, at the conclusion of the registry, reports will be written detailing the registry's findings.

Figure 1. Entry into the COVID-19 vaccine pregnancy registry

* For novel platforms like mRNA consider a longer time frame exposure preconception ?3months

Figure 2 describes the v-safe after vaccination health checker pregnancy ascertainment questions and among participants who report a pregnancy, the follow-up contacts and surveys from the COVID-19 vaccine pregnancy registry call center.

The 1st box on the top right of figure 2 describes the pregnancy screening process for participants in the v-safe after vaccination health checker who identified as female. Female participants are asked pregnancy screening questions at the initial v-safe health survey, and at day 21, 42, and 3, 6, 12 months after most recent vaccine dose. If the participant answers "don't know" to the initial health survey pregnancy screening question and no longer participates in v-safe health check-ins, she will be contacted by the pregnancy call center within 3 months to confirm pregnancy status. Following the illustration in the diagram, the top-left blue box describes the 1st v-safe health check-in question. Female participants could answer "no/don't know" or "yes" to the initial pregnancy status screening question. If the reply is "no/don't know", they will be screened at each subsequent (at day 21, 42, and 3, 6, 12 months) v-safe health check-in (2nd box). If the response is "no" (3rd box), the remaining v-safe health check-in questions will resume according to schedule.

Active follow-up by the COVID-19 pregnancy registry call center ensues if the participant response to pregnancy status is "yes" at the initial or subsequent screening to confirm pregnancy status (1st green box). A "yes" reply confirming pregnancy status is followed by an initial call center pregnancy survey (2nd 'green' box), brief checkin every trimester (3rd "green box), active post-partum follow-up (4th 'green' box). The final (5th 'green box) includes obtaining medical records if permission is provided. A "no" reply will loop back to resuming v-safe health check-ins according to schedule (last 'blue' box on the left).

References:

- 1. https://www.fda.gov/media/144337/download
- 2. https://www.fda.gov/media/144585/download
- 3. https://www.cdc.gov/vaccines/acip/meetings/downloads/slides-2020-12/COVID-05-Vote.pdf
- 4. https://www.cdc.gov/vaccines/acip/meetings/downloads/slides-2020-10/COVID-Wallace.pdf
- 5. https://www.cdc.gov/mmwr/volumes/69/wr/mm695152e2.htm?s_cid=mm695152e2_w
- 6. https://www.fda.gov/media/144414/download
- 7. https://www.cdc.gov/coronavirus/2019-ncov/vaccines/recommendations/pregnancy.html
- 8. https://www.cdc.gov/vaccines/acip/meetings/downloads/slides-2020-12/slides-12-12/COVID-03- Mbaeyi.pdf
- 9. https://www.fda.gov/emergency-preparedness-and-response/coronavirus-disease-2019-covid-19/janssen-covid-19-vaccine

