Therefore, CDC developed an active smartphone-based surveillance system, or v-safe, to support the work of the Immunization Safety Office (11). v-safe uses text messages with embedded web surveys to collect information on adverse health events and side effects following COVID-19 vaccination (11). Included in the web surveys are questions about pregnancy status at the time of vaccination or shortly after vaccination (11). Participants who indicated receipt of a COVID-19 vaccine during pregnancy or 30 days before the last menstrual period were eligible to be contacted by telephone to enroll in the CDC COVID-19 Vaccine Pregnancy Registry (11). Eligibility for the pregnancy registry was cut-off on June 18, 2021. Individuals who reported pregnancies into v-safe after June 18, 2021 were not included in the potential participant pool due to the volume of participants who reported pregnancies to v-safe. People who chose to participate in the COVID-19 Vaccine Pregnancy Registry were asked questions about pregnancy health conditions, pregnancy outcomes, delivery and postpartum complications, health history, and demographics. Participants who reported live births were asked questions about their infants' health, including any diagnoses of health conditions such as birth defects, hospitalizations, or referrals to specialists, when their infant was at least 3 months old. Information about the participants' and their infants' medical providers was also collected. The COVID-19 Vaccine Pregnancy Registry began enrollment on January 11, 2021 and continued through about August 31, 2022. As of August 31, 2022, a total of 22,952 participants were enrolled into the COVID-19 Vaccine Pregnancy Registry, representing 22,967 pregnancies of which 20,772 had live births. Birth outcome was unknown for 1,179 participants due to participant withdrawal, loss to follow-up (missed 2 sequential scheduled calls), or timed out of last scheduled call (these outcomes may be collected during the 15-month follow up call).

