
The initial contact will collect pregnancy history information, including outcomes of prior pregnancies, the gestational dating of the vaccine-exposed pregnancy, and pregnancy and postpartum complications or comorbidities. Previously, call center follow-up interviews occurred once every trimester to identify any pregnancy complications, and a follow-up interview occurred at 4-8 weeks postpartum to obtain information on the delivery, any potential complications in the participant or infant, and to request consent from the participant for release of her and the infant's medical records. By the end of February 2022, all pregnancies reported to v-safe that were included in the pool of potential pregnancy registry participants had ended by the time of initial contact. This was due to resource constraints and the fact that the estimated due date for the pregnancy reported to v-safe was unknown prior to the initial outreach from the pregnancy registry call center. Therefore, for over half of enrolled registry participants, all information about the pregnancy and outcome was collected at the time of the registry's initial outreach. A brief call center follow-up interview occurred when the infant was 3 months old to inquire about any adverse events, including the diagnosis of any birth defects. If the initial call occurred when the infant was older than 3 months old, this information was obtained at the initial call as well. Finally, in the 2nd phase of the registry, focused on the participants' and infants' health in the year following the end of the pregnancy, a single interview will be conducted for the time period through 15 months following the end of the pregnancy. This interview will be administered, when the infant is at least 16 months old to ensure a consistent amount of time has passed since delivery. Participants will be asked about their health status as well as their infant's, including any birth defect diagnoses, infant medical conditions, COVID-19 infections, and hospitalizations, during that 15-month period. Participants who experienced a pregnancy

outcome other than a live birth (e.g., stillbirth, spontaneous abortion, induced abortion, ectopic pregnancy) or have already shared that their infant is deceased will only be asked the set of questions about maternal health. Participants whose pregnancy outcome is not yet known at the time of the 15-month interview will additionally be asked questions about their pregnancy outcome.

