For the 15-month follow-up interview, we will use the cohort of pregnant people enrolled in the COVID-19 Vaccine Pregnancy Registry during January 11, 2021—August 31, 2022 (n=22,952 participants; this includes 15 participants who had more than one eligible pregnancy). Of these, we exclude participants who 1) withdrew participation (n=35), 2) indicated that they did not want to be contacted by the registry in the future (responded "no" in the survey for a question asking permission to contact them in the future, n=244), 3) were lost to follow up (missed 2 scheduled calls, n=417), or 4) were deemed ineligible based on vaccination occurring more than 30 days prior to pregnancy onset (n=72). In total, there are approximately 22,203_participants (22,216 pregnancies, 92% with known live birth) eligible for the 15-month follow-up interview. Because participants have already engaged with the pregnancy registry, we expect the number lost to follow-up (LTFU) to be minimal. A 10% LTFU rate would result in a sample size of approximately 19,982 participants, and a 20% LTFU rate would result in a sample size of approximately 17,762_participants.

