Ongoing data quality checks occur to identify errors, including implausible and missing values. Data from the pregnancy registry are analyzed monthly at minimum. Reports include descriptive analyses of any adverse outcomes and rates of follow up among pregnant persons. Specifically, rates are calculated for fetal demise (spontaneous abortion and stillbirth), pregnancy complications (pregnancy induced hypertension, gestational diabetes, pre-eclampsia), adverse birth outcomes (preterm delivery, small for gestational age, low birth weight, neonatal intensive care unit stays), major birth defects, and other outcomes of interest. These proportions may be compared to national averages, published background rates or estimates seen in other data systems with similar demographics. For outcomes that may undergo clinical review and adjudication, sensitivity analyses will be performed that account for any potential recategorization of outcomes following the clinical adjudication processes (clinical review of participant-reported data and/or medical record data by clinical SMEs). Adverse events may be analyzed in aggregate if rare (i.e., any major cardiac defect). Any potential safety signals will be compared to other surveillance systems, such as VAERS, and specifically for birth defects, the CDC's Metropolitan Atlanta Congenital Defects Program or the Texas Birth Defects Registry (19, 20). Persistent signals will be evaluated using more robust surveillance system data (such as the Vaccine Safety Datalink) that have denominator data of pregnant persons who received COVID-19 vaccines and comparison groups of pregnant persons who did not receive COVID-19 vaccines. For rare outcomes, evaluations may also be conducted in other database systems, such as the FDA or the Department of Defense (DOD), for appropriate follow up assessment.

Because we do not have a control group and the pregnancy registry is not nationally-representative, we will compare characteristics of pregnancy registry participants with those of representative samples of pregnant people within the United States to aid in the interpretation of generalizability. For example, we may compare the outcomes with already collected data from other surveillance systems, such as the Pregnancy Risk Assessment Monitoring System or Vaccine Safety Datalink or compare to background rates in the literature.

Outcomes:

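### More pregnancies have an unknown outcome (1,179) than any known non-live outcome (1,016); the 15-month call can recover only some of them, and no named sensitivity analysis covers the rest

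*Protocol*

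**What the plan says.** All references are to the Protocol; no separate statistical analysis plan is at hand.

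- **Background, status at 31 August 2022.** "a total of 22,952 participants were enrolled into the COVID-19 Vaccine Pregnancy Registry, representing 22,967 pregnancies of which 20,772 had live births". Then: "Birth outcome was unknown for 1,179 participants due to participant withdrawal, loss to follow-up (missed 2 sequential scheduled calls", with a third cause: "timed out of last scheduled call (these outcomes may be collected during the 15-month follow up call".
- **Data collection (call center and registry).** "Participants whose pregnancy outcome is not yet known at the time of the 15-month interview will additionally be asked questions about their pregnancy outcome". The same section lists stillbirth, spontaneous abortion, induced abortion and ectopic pregnancy as outcomes other than live birth. It also says that for over half of enrolled participants everything about the pregnancy and its outcome was obtained at first contact.
- **Data collection, cohort for the 15-month interview.** Four groups are removed: those who "withdrew participation (n=35", those who declined future contact (244), those lost after missing two calls (417) and those found ineligible (72).
- **Analysis plan.** "rates are calculated for fetal demise (spontaneous abortion and stillbirth" among other outcomes. These are then called proportions that may be compared with national or published background figures. One sensitivity analysis is named, for outcomes reclassified at adjudication.
- **Limitations and challenges.** Limited retention is listed. A second sensitivity analysis is named, restricted to participants enrolled and followed before an adverse outcome.
- **Human subject considerations.** For anyone who opts out, "their data will only be used for the time they were considered an active participant".

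**The concern.** Fetal demise is a minority outcome, so a modest number of missing outcomes can matter a great deal to its estimate. Here the missing outcomes outnumber everything recorded on the non-live side. Drop-out may also depend on the outcome, since a scheduled call after a pregnancy loss is one a participant may choose not to answer. If so, a proportion among known outcomes is too low, and a proportion that leaves the unknowns in the denominator as event-free is lower still. The comparison with background rates would then lean towards false reassurance.

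The selection bias discussed under Limitations, towards people with concerns or adverse events, works in the other direction, so it gives no warning of this. The two sensitivity analyses deal with reclassification and with enrolment timing. Neither deals with participants who left before an outcome was recorded.

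**Working it through.** **Inputs.** From the Background: 22,952 participants, 22,967 pregnancies, 20,772 with live birth, 1,179 unknown. From Data collection: exclusions of 35, 244, 417 and 72; about 22,203 participants (22,216 pregnancies, 92% known live birth) eligible for the 15-month interview.

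**1. The plan's own figures.** 22,952 − 35 − 244 − 417 − 72 = 22,184, against about 22,203 stated. The gap of 19 would be explained by overlapping exclusion reasons. 22,203 × 0.9 = 19,982.7 and 22,203 × 0.8 = 17,762.4, as stated for 10% and 20% loss.

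**2. Known non-live outcomes.** 22,967 − 20,772 − 1,179 = 1,016. The unknowns are counted in participants, but on a participant base the result is 22,952 − 20,772 − 1,179 = 1,001, so the ordering is unchanged. Unknown share: 1,179 / 22,967 = 5.1%.

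**3. Non-live share under different treatments of the unknowns.** Known rate r = 1,016 / (22,967 − 1,179) = 1,016 / 21,788 = 4.66%. With unknowns non-live at m times r, the share is (1,016 + 1,179 × m × r) / 22,967.

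| Treatment of the 1,179 | Non-live share |
|---|---|
| All live (kept as event-free) | 1,016 / 22,967 = 4.42% |
| Dropped, or m = 1 | 4.66% |
| m = 2 (assumed) | 4.90% |
| m = 3 (assumed) | 5.14% |
| m = 5 (assumed) | 5.62% |
| All non-live | (1,016 + 1,179) / 22,967 = 9.56% |

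**4. After the 15-month call.** Suppose all 35 + 417 = 452 withdrawn or lost participants have unknown outcomes. Then 1,179 − 452 = 727 (62%) could at most still be called. If all 727 are reached and had a live birth, the bound is (1,016 + 452) / 22,967 = 6.39%. If 80% are reached, 452 + 0.2 × 727 = 597.4 stay unknown and the bound is 7.02%.

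**5. Is 452 plausible?** The pregnancies excluded from the call that are not known live births number 2,195 − 22,216 × (1 − q), where 2,195 = 22,967 − 20,772 and q is the known-live share. For q = 91.5%, 92% and 92.5% this gives about 307, 418 and 529. So 452 fits within the rounding of 92%. It also rules out all 696 withdrawn, lost or no-contact participants being unknown. With 529 the bound in step 4 would be (1,016 + 529) / 22,967 = 6.73%.

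**6. Where the unknowns sit.** Over half of participants gave their outcome at first contact, so on that reading the unknowns come from the remainder, fewer than 22,952 / 2 = 11,476 people. That makes them at least 1,179 / 11,476 = 10.3% of that group. The sensitivity analysis named under Limitations draws on this group, so it carries about twice the missingness of the whole registry.

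**The case against.** The strongest reply is that the Protocol does provide for unknown outcomes. The Background sentence itself foresees collecting them later, Data collection commits to asking, and the regular reports include rates of follow-up. This stands, and a reader who infers that drop-out is ignored goes too far. But the call omits the withdrawn and the lost, so recovery is partial. The remark in the Background could be read as covering only the timed-out group. On that reading the two sections do not conflict, but the withdrawn and lost are then left with no route to recovery at all.

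Second, a reader might infer that the plan fixes a simple proportion for fetal demise. It does not: it uses both rates and proportions and sets no denominator, censoring rule or estimator. A separate analysis plan could settle this. The opt-out clause on data use is compatible with censoring. What remains is that the Protocol's own Analysis plan chooses which sensitivity analyses to name and leaves this one out.

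Third, a reader might take 1,016 as the fetal-demise count. It is not, because it includes induced abortion and ectopic pregnancy, and the Protocol gives no split. The percentages show the scale of the missingness; they do not bound a planned estimate.

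Fourth, comparison with background rates is optional, the later objectives concern infants and maternal conditions, and persistent signals go to systems with unvaccinated comparators. That limits the consequence. It does not remove it, because a rate biased low may never raise the signal that would be passed on.

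**Conclusion.** The point holds in a limited form. Outcomes are unknown for 5.1% of pregnancies, more than all known non-live outcomes together. The planned recovery leaves out groups that the Protocol itself names as sources of the unknowns, and no named sensitivity analysis covers what stays unknown.

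Under assumed multiples of 3 and 5, the non-live share moves from 4.7% to 5.1% and 5.6%, a shift of about 0.5 to 1.0 percentage points. The 9.6% figure is a logical limit before recovery and should not be read as a likely value. The figure of about 6.4% rests on all 452 withdrawn or lost participants being unknown and staying so, and on everyone else being reached and having had a live birth. The documents do not show that drop-out is related to loss, nor that any reported rate is in fact biased. They show that the plan would not reveal it if it were. The change is worth making but does not undermine the registry.

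**What to change.** In the Analysis plan:

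- Estimate fetal demise by a gestational-age life table with delayed entry at enrolment and censoring at last contact. Report participants enrolled after the pregnancy ended separately, since they contribute no prospective time at risk.
- Because that censoring may itself be informative, add a sensitivity range. This is the essential part. Take unknown outcomes as non-live at 1, 2, 3 and 5 times the observed proportion, plus the all-live and all-non-live bounds, and recompute after the 15-month calls.
- Print the number of unknown outcomes beside each pregnancy-outcome rate, and define the denominator.

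In the Background and Data collection, reconcile the statement that unknown outcomes may be collected at the 15-month call with the exclusion of withdrawn, no-contact and lost participants, and say how many unknown outcomes remain open to recovery.

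The cost is wording and modest programming. Gestational dating is already collected at first contact; that dates of last contact are held is assumed. The downside is a wider and less favourable stated uncertainty.

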3b. To monitor infant COVID-19 vaccination and characterize participant-report of infant adverse effects following COVID-19 vaccination

Objective 4: Among persons who received COVID-19 vaccination during pregnancy, evaluate risks for pregnancyrelated medical conditions, including thromboembolic events, as well as new autoimmune conditions, and heart conditions, in the first 15 months postpartum.

Methods:

Surveillance Population and Inclusion Criteria

The population of pregnant persons eligible for surveillance through the pregnancy registry will include those exposed to COVID-19 vaccines during pregnancy or in the periconception period (30 days before LMP through 14 days after LMP) (Figure 1). Additional data will be collected on these pregnant persons; infants born to these persons will be monitored for the first 15 months of life to identify any newborn and infant complications and diagnoses of major birth defects. Persons who are found not to be pregnant at the time of vaccination and are not identified as pregnant within 30 days after vaccination will not be included in the registry. There may be participants who are initially determined to be eligible based on their reported LMP during the first interview

but may later be deemed to be ineligible if gestational age estimation is updated over the course of pregnancy. These participants will be excluded from outcome analyses and the 15-month follow-up survey (n=70).

Identification of exposed pregnancies

The v-safe After Vaccination Health Checker system is an opt-in text messaging and web-based surveillance system that is offered to COVID-19 vaccine recipients. As part of the initial v-safe survey, all non-male participants (i.e., female, prefer not to say, other) will be asked questions about pregnancy status. In addition, screening questions to identify potential pregnancies will be asked at v-safe health check-ins that occur at days 21 and 42 after each vaccine dose (if applicable) and at 3, 6, and 12 months after the last vaccine dose (Figure 2). V-safe data managers at CDC will notify the pregnancy call center team (described below) of potential pregnant vaccine recipients. The pregnancy call center will be staffed by individuals trained to administer the questionnaire and on the handling of PII. To identify as many pregnant persons as possible through v-safe, the follow up plan is:

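### The 15-month interview leaves out 417 participants whose only stated fault is two missed scheduled calls; calling them costs little and would reduce possibly informative missingness

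*Protocol*

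**What the plan says.** The Data collection section starts the 15-month cohort from everyone enrolled ("n=22,952 participants; this includes 15 participants who had more than one eligible pregnancy") and removes four groups:

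- those who "withdrew participation (n=35");
- those who answered no to a "question asking permission to contact them in the future, n=244");
- those who "were lost to follow up (missed 2 scheduled calls, n=417");
- 72 participants found ineligible because vaccination was too long before pregnancy.

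It then gives "approximately 22,203_participants (22,216 pregnancies, 92% with known live birth) eligible for the 15-month follow-up interview", and sizes of 19,982 and 17,762 under 10% and 20% loss.

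The Background section reports 1,179 participants with unknown birth outcome. It gives three causes: withdrawal, loss to follow-up (two sequential missed calls), and timing out of the last scheduled call. It closes with the remark that "these outcomes may be collected during the 15-month follow up call".

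Surveillance Population and Inclusion Criteria mentions participants who become ineligible when gestational age is revised: "These participants will be excluded from outcome analyses and the 15-month follow-up survey (n=70").

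**The concern.** The 417 are dropped for non-response, not refusal. The protocol gives no reason for treating them differently from timed-out participants, whose outcomes may be just as unknown and who remain eligible. The means to call them already exist in the Data collection section: outcome questions for anyone whose pregnancy outcome is unknown, the estimated due date as call anchor when the outcome date is missing, and a limit of six attempts.

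People who stop answering around delivery may do so because of what happened at delivery. If so, dropping them by rule makes the missingness informative in a way that a few calls could partly repair. The group also contributes nothing on infant or maternal health through 15 months.

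The exclusion also makes retention look better. The protocol expects minimal loss because participants have already engaged with the registry, but it says so after removing those already lost.

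**Working it through.** **Inputs.** From Data collection: 22,952 participants; exclusions of 35, 244, 417 and 72; 22,203 eligible participants with 22,216 pregnancies; at most 6 attempts each. From Background: 1,179 unknown outcomes, and enrolment "representing 22,967 pregnancies of which 20,772 had live births".

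**1. The plan's own figures.**
- Loss scenarios: 22,203 × 0.9 = 19,982.7 and 22,203 × 0.8 = 17,762.4. Both agree with the stated sizes.
- Listed exclusions: 35 + 244 + 417 + 72 = 768, and 22,952 − 768 = 22,184.
- Implied exclusions: 22,952 − 22,203 = 749. The gap is 768 − 749 = 19 people, or 19/22,203 = 0.09%. If 19 people each fall in two categories, 22,203 is exact.
- Pregnancies: 22,967 − 22,216 = 751 removed with 749 participants, so extra pregnancies fall from 15 to 13, and 22,203 + 13 = 22,216. This is coherent.

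**2. Size of the excluded group.**
- Share of enrolled: 417/22,952 = 1.8%.
- Share of unknown outcomes: 417/1,179 = 35.4%. This is a maximum, reached only if every one of the 417 has an unknown outcome.

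**3. Bounds on the non-live-birth proportion, assuming all 417 are unknown.**
- Known non-live-birth outcomes: 22,967 − 20,772 − 1,179 = 1,016, treating each unknown participant as one pregnancy.
- Current proportion among known outcomes: 1,016/(20,772 + 1,016) = 1,016/21,788 = 4.7%.
- All 417 live births: 1,016/22,205 = 4.6%.
- All 417 non-live births: (1,016 + 417)/22,205 = 1,433/22,205 = 6.5%.

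These are extremes, not predictions.

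**4. Is that assumption plausible?** 92% of 22,216 is about 20,439 known live births, so about 20,772 − 20,439 = 333 of the 751 removed pregnancies had a known live birth and about 418 did not. Rounding of the 92% (91.5% to 92.5%) allows 307 to 529. The figure covers all four exclusion groups and includes known losses, so it is suggestive only.

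**5. Cohort with the 417 restored.**
- Lower: 22,952 − 35 − 244 − 72 = 22,601. This applies with no overlap, or if all 19 overlaps involve the 417, so that 398 return.
- Upper: 22,203 + 417 = 22,620, if no overlap involves the 417.
- At 10% loss: 20,341 to 20,358. At 20% loss: 18,081 to 18,096.

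**6. Retention against the restored base.** With 19,982.7 reached, cumulative loss is 11.6% (base 22,601) to 11.7% (base 22,620), not 10%. With 17,762.4 reached, it is 21.4% to 21.5%, not 20%.

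**7. Cost.** 417 × 6 = 2,502 attempts at most, against 22,203 × 6 = 133,218, or 1.9%.

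**The case against.** **No contradiction is forced.** A reader might infer that the protocol promises to collect the outcomes of the 417 and then refuses to call them. The Background remark directly follows the timed-out group and may cover that group alone. Read as covering all three causes, it would also take in people who withdrew. It says only that outcomes may be collected. Even if all 35 withdrawn and all 417 lost participants had unknown outcomes, 1,179 − 35 − 417 = 727 (62%) would be left, before any removed by the other two exclusions, so the remark can be true with the 417 excluded. This stands. The wording needs clarifying, and the case for calling the 417 does not rest on it.

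**There is a related rule.** The Unreachable section drops from the phone survey anyone not reached in six attempts a week apart, and the protocol cites resource constraints. Dropping earlier non-responders is in keeping with that. But the 417 are defined by two missed scheduled calls, and nothing says that each missed call meant six failed attempts.

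**The prospective group.** A reader might infer that only people enrolled during pregnancy can miss two calls, so that the exclusion thins the group behind the sensitivity analysis in Limitations and challenges. The protocol does not establish this. Calls were also scheduled at 4–8 weeks postpartum and at 3 months, so someone enrolled soon after delivery, with outcome known, could miss both.

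**The target is indirect.** The bounds concern the non-live-birth proportion, while Phase 2 mainly concerns infant and maternal health through 15 months. No effect on those outcomes has been computed. Calling people who already missed two calls will reach only some of them, and the protocol gives no basis for a yield. Both points stand and limit the claim.

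**Conclusion.** The exclusion of the 417 is real, is not justified in the text, and is cheap to undo. It is a worthwhile improvement, not a fatal flaw: 1.8% of those enrolled, set beside the 10% to 20% further loss that the protocol already considers. Harm requires that missed calls relate to outcome, which the documents neither show nor rule out. The 35% share and the 4.6% to 6.5% range hold only if all 417 have unknown outcomes, and the upper end also needs every one to be a non-live birth.

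On the counts, a reader might infer that 22,203 is wrong and that 22,184 should replace it. The documents do not support this: the total is labelled approximate, 19 overlapping exclusions would explain it exactly, and the pregnancy count and both loss scenarios agree with it. What is missing is a statement on overlap. The ineligible counts of 70 and 72 are unexplained; the second may be defined more broadly, but the text does not say so. Both are editorial.

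**What to change.** - Delete the third exclusion. Attempt the 417 under the existing six-attempt limit, using the pregnancy-outcome questions already planned. Keep excluding anyone who withdrew, declined future contact or is ineligible, including any of the 417 who also fall in those groups.
- Restate the eligible cohort at about 22,601 to 22,620, settled by the overlap count, with 20,341–20,358 at 10% loss and 18,081–18,096 at 20% loss.
- State in Background which unknown outcomes can be collected at the 15-month call, and reword the Unreachable section so that it does not bar the renewed attempt.
- Add a flow table with unique counts per exclusion (768 listed, 749 implied), and use one ineligible count or explain 70 and 72.

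The cost is protocol wording, at most about 1.9% more call attempts by the existing call center, and a slightly higher reported loss rate. If the sponsor keeps the exclusion, it should give the reason and correct the Background remark.
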